3.0 PATIENT ELIGIBILITY

3.1 Inclusion Criteria

Subjects must meet all of the inclusion criteria to participate in this study.

1. Patient able to understand and the willingness to sign a written informed consent.
2. Pathologically-confirmed solid tumor or hematologic malignancy with symptomatic bone metastases.
3. Patient is planned to receive hypofractionated palliative radiation ≤ 10 fractions.
4. Patient must be opioid-tolerant (greater than or equal to 60mg morphine or equivalent) and on a stable dose of oral opioids for greater than or equal to 1 week. Stable baseline opioid dosage defined as a dosage that does not fluctuate by more than 50% from the average dosage over one week prior to screening.
5. Patient must be on a stable dose of adjuvant pain therapies for one week prior to screening or after 4-5 half-lives of adjuvant pain therapies (i.e., glucocorticoids, NSAIDs, anticonvulsants, pharmaceutical cannabinoids, tricyclic antidepressants).
6. Patient is ≥ 18 years of age.
7. Both men and women of all races and ethnic groups are eligible for this trial.
8. ECOG Performance Status ≤ 3 (see **Appendix A**)
9. Women of child-bearing potential and men with partners of child-bearing potential must agree to use adequate contraception (hormonal or barrier method of birth control; abstinence) prior to study entry, for the duration of study participation, and for 28 days following completion of therapy. Should a woman become pregnant or suspect she is pregnant while participating in this study, she should inform her treating physician immediately.
 - A woman of child-bearing potential is any female (regardless of sexual orientation, having undergone a tubal ligation, or remaining celibate by choice) who meets the following criteria:

- Has not undergone a hysterectomy or bilateral oophorectomy; or
10. Has not been naturally postmenopausal for at least 12 consecutive months (i.e., has had menses at any time in the preceding 12 consecutive months). Women of child-bearing potential has negative pregnancy test prior to initiating study drug dosing.

3.2 Exclusion Criteria

Subjects meeting any of the exclusion criteria at baseline will be excluded from study participation.

1. Patient is currently receiving or has received another investigational agent within 30 days or monoamine oxidase inhibitor within 14 days prior to Lazanda administration.
2. Patients who require immobilization with a thermoplastic mask for radiation treatment.
3. Patient is planned to receive interventional procedures (i.e. surgery) that may affect study outcomes.
4. Patient has a history of hypersensitivity to fentanyl or opioids.
5. Patient is pregnant or nursing. There is a potential for congenital abnormalities and for this regimen to harm nursing infants.
6. Patient is being treated with oxymetazoline for allergic rhinitis or has a disorder or current medication use likely to adversely affect normal functioning of the nasal mucosa.
7. Patient has uncontrolled or rapidly escalating background pain.
8. Patient has bradyarrhythmia.
9. Patient is considered medically unstable.
10. Patient is thought to be at risk for misuse, abuse, addiction or overdose for Schedule II controlled substance, as evidenced by the following:
 - a. An Opioid Risk Tool (ORT) score of greater/less than or equal to 8.²
 - b. A review of the California Prescription Control Monitoring Program (PDMP) Controlled Substance Utilization Review and Evaluation System (CURES) report demonstrates multiple prescribing providers and/or multiple pharmacies in the last 30 days. The CURES report will also be used to verify opioid use, opioid dose, and current prescribing providers.

4.0 TREATMENT PLAN

4.1 Study Design

This is a phase II, single-center, open-label study. We anticipate recruitment of approximately 15 total study participants at the UCSD Moores Cancer Center. Study participants will be recruited across all oncology disease teams. Potential participants will be identified in weekly palliative care or disease team patient triage meetings.

To meet eligibility for participation, a patient must be greater than or equal to 18 years old, have histologically-confirmed cancer with symptomatic bone metastases, an ECOG performance

status less than or equal to 3, and are planned to receive hypofractionated palliative radiation less than or equal to 10 fractions. Qualifying subjects must be opioid-tolerant, defined as greater than or equal to 60mg morphine or equivalent, and be on a stable dose of oral opioids for greater than or equal to 1 week. Stable baseline opioid dosage is defined as a dosage that does not fluctuate by more than 50% from the average dosage over one week prior to screening. Patients must also be on a stable dose of adjuvant pain therapies for one week prior to screening or after 4-5 half-lives of adjuvant pain therapies. Patients will be excluded if they are receiving or have received another investigational agent within 30 days or monoamine oxidase inhibitor within 14 days prior to Lazanda administration, have known hypersensitivity to fentanyl or opioids, have known, planned interventional procedures such as surgery that may affect study outcomes, are pregnant or nursing, have a disorder or current medication use likely to adversely affect normal functioning of the nasal mucosa, have uncontrolled or rapidly escalating background pain, or are medically unstable.

The primary objective of this study is to assess the change in patient reported positional pain intensity (PI) as measured by an 11-point numerical rating scale (NRS-11) (**Appendix C**) in cancer patients with bone metastases assessed at a simulation visit and each subsequent daily palliative radiation fraction. Our primary objective will be measured using the pain intensity difference (PID) of the NRS-11 from the time of laying down on the hard surface (0 minutes) to the 15 minutes after laying down on the hard surface timepoint at baseline (the simulation visit) and at each subsequent study visit ($PID_{15} = PI_0 - PI_{15}$).

Secondary objectives will seek to assess patient reported pain severity using the BPI-sf (**Appendix D**), and evaluate adverse effects associated with Lazanda use utilizing the NCI CTCAE version 4.03 before and after palliative radiation.

Exploratory objectives will assess the impact on radiation treatment delivery efficiency, which will be quantified by determining the total time of radiation treatment, defined as the average time on the treatment table for each fractionation visit. A second exploratory objective will be to examine the effect of: baseline pain intensity score, 24-hour opioid use (oral morphine equivalents) and total treatment time at each fraction (minutes) on change in pain intensity (PID15)

After obtaining written informed consent, patients will have the following procedures completed to confirm eligibility: physical exam with vital signs and weight, ECOG performance status, comprehensive metabolic panel, and a serum pregnancy test (women of child-bearing potential only). During this screening period, patients will also complete a baseline NRS pain score and BPI-sf questionnaire (**Appendix D**), and report baseline 24-hour opioid dose.

Event	NRS-11	BPI-sf	Diaries		
			Medication Use	Nausea Vomiting	Laxation
Simulation	T-15, T0, T+15	T15+	X	X	X
Daily radiation fraction	T-15, T0, T+15	T15+	X	X	X

Table 1: Summary of Assessments; NRS-11 = numerical rating scale; BPI-sf = Brief Pain Inventory short form; T-15= 15 minutes prior; T0=at point of laying down; T+15 = 15 minutes after layind down; T15+ = any point after 15 minutes from laying down; X = once daily

Simulation Evaluation

The subject will then undergo radiation therapy simulation procedures (within approximately 2 weeks of radiation therapy) followed by hypofractionated radiation therapy, according to UCSD Radiation Oncology standard procedure and treatment plan determined by the subject’s radiation oncologist. During radiation simulation and daily during each visit to the radiation center for hypofractionation delivery, subjects will have vital signs and weight collected per routine care. An ECOG performance status will also be assessed daily during radiation therapy. At the time of radiation simulation and daily during radiation therapy, subjects will complete the BPI-sf (**Appendix D**), Medication Use Diary (**Appendix E**), Laxation Diary (**Appendix F**), and Nausea/Vomiting Diary (**Appendix G**). NRS pain scores will also be collected at three time points during each visit to the radiation center: 15 minutes prior to laying on the hard surface (T-15), at the time of laying on the hard surface (T0), and at 15 minutes after laying on the hard surface(T+15). Exact time of each pain score rating will also be collected. The study coordinator will record total time in radiation therapy unit and total recumbent time (time laying down) during the simulation and each radiation treatment visit. Additionally, radiation treatment parameters, the presence of any adverse effects (NCI CTCAE v 4.03), and concomitant medications will be recorded.

Lazanda Dosing During Simulation

Subjects will receive study drug, Lazanda at 100mcg dose, 15 minutes prior to simulation (T-15) at the radiation therapy simulation visit. Lazanda dose titration will follow the guidelines as indicated in the product package insert from the radiation simulation visit through the end of radiation therapy. Lazanda dose titration procedures are further detailed in **Section 4.2**.

Subjects will undergo a post treatment follow-up period after completion of their radiation therapy. During this follow-up period, subjects will complete the BPI-sf (**Appendix D**), Medication Use Diary (**Appendix E**), Laxation Diary (**Appendix F**), and Nausea/Vomiting Diary (**Appendix G**) daily for 2 days. Concomitant medication use will also be recorded. Subjects will be monitored for the presence of any adverse effects (NCI CTCAE v 4.03) until 28 days following their last dose of Lazanda.

4.2 Treatment Dosage and Administration

Study drug, Lazanda, will be self-administered intranasally during this study. The dose of Lazanda is not predicted from the daily maintenance dose of opioid used to manage persistent cancer pain and must be determined by dose titration. Due to differences in pharmacokinetic

properties and individual variability, do not switch patients on a mcg per mcg basis from any other fentanyl product as Lazanda is not equivalent with any other fentanyl product.

4.2.1 Radiation Simulation Visit(s)

To determine an individual patient's effective and tolerable Lazanda dose, each subject will undergo dose titration during the radiation simulation visit. Lazanda dose for all subjects on study, including those switching from another fentanyl product, will be determined according to the following procedures:

- 15 minutes prior (T-15) to beginning the radiation therapy simulation, subjects will receive an initial dose of 100 mcg (1 spray) of Lazanda in one nostril prior to lying on the CT simulation hard surface.
- If adequate analgesia is obtained within 30 minutes of administration of the 100-mcg single spray, subsequent pain episodes will be treated with this dose.
- If the subject does not experience relief after 30 minutes, he or she may take another 100 mcg in the opposite nostril **but must wait at least 2 hours** (i.e., T-15 + 2 hours) from the first spray before administering this second 100 mcg dose. The subject may delay or reschedule the simulation (within a 14 days period) or radiation delivery to achieve the adequate pain control dose.
- If adequate analgesia is still not achieved, the subject will continue to dose escalate in a step-wise manner at a minimum of 2 hours between each subsequent escalation until adequate analgesia with tolerable side effects is achieved. A maximum of 4 doses or 400 mcg allowed per day.
- Dose titration steps are further detailed in **Table 1**.

Table 1: Lazanda Dose Titration Steps

Lazanda Dose	Using
100 mcg	1 x 100 mcg spray
200 mcg	2 x 100 mcg spray (1 in each nostril)
400 mcg	4 x 100 mcg spray (2 in each nostril, alternate nostrils) or 1 x 400 mcg spray

Each bottle contains a total of 8 sprays. Lazanda bottles come in 100 mcg or 400 mcg dose. If using dose of 100 mcg with the 100-mcg spray, the patient would have total of 8 doses in a single bottle. If using dose of 200 mcg with the 100-mcg spray, the patient would have total of 4 doses in a single bottle. If using dose of 400 mcg with the 100-mcg spray, the patient would have total of 2 doses in a single bottle. Alternately, if using a bottle of the 400-mcg spray at a dose of 400 mcg, the patient would have total of 8 doses in a single bottle.

Lazanda titration should be done with caution in patients with chronic obstructive pulmonary disease or preexisting medical conditions predisposing them to respiratory depression and in patients susceptible to intracranial effects of CO₂ retention. Caution should also be used in patients on central nervous system (CNS) depressants and potent CYP3A4 inhibitors.

The minimal effective intranasal dose from the radiation therapy simulation will be the dose used as pre-medication prior to any further radiation therapy fractions (up to 10 fractions). Lazanda should be administered 15 (T-15) minutes prior to laying on the hard surface for each simulation visit. If the response to the titrated Lazanda dose markedly changes, an adjustment of dose may be necessary to ensure that an appropriate dose is maintained as deemed by the investigator.

Subjects will be instructed on the proper use of Lazanda as follows:

- 1) Prime the device before use by spraying into the pouch (4 sprays in total). If study drug has not been used for 5 days, re-prime by spraying once.
- 2) Insert the nozzle of the Lazanda bottle a short distance (about ½ inch) into the nose and point towards the bridge of the nose, tilting the bottle slightly.
- 3) Press down firmly on the finger grips until hearing a “click” and the number in the counting window advances by one.

Subjects will also be advised that the fine mist spray is not always felt on the nasal mucous membrane and to rely on the audible click and advancement of the dose counter to confirm a spray have been administered.

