	
pain therapies (i.e., glucocorticoids, NSAIDs, anticonvulsants, pharmaceutical cannabinoids, tricyclic antidepressants).
 
 4. Patient is ≥ 18 years of age. 5. ECOG Performance Status ≤ 3 6. Negative pregnancy test prior to initiating study treatment for females of childbearing potential. 
Key Exclusion Criteria
 
 1. Patient is currently receiving or has received another investigational agent within 30 days or monoamine oxidase inhibitor within 14 days prior to study drug administration. 2. Patients who require immobilization with a thermoplastic mask for radiation treatment. 3. Patient is planned to receive interventional procedures (i.e., surgery) that may affect study outcomes. 4. Patient has a history of hypersensitivity to fentanyl or opioids. 5. Patient is pregnant or nursing. 6. Patient is being treated with oxymetazoline for allergic rhinitis or has a disorder or current medication use likely to adversely affect normal functioning of the nasal mucosa. 7. Patient has uncontrolled or rapidly escalating background pain. 8. Patient has bradyarrhythmia. 9. Patient is medically unstable. 10. Patient is thought to be at risk for misuse, abuse, addiction or overdose for Schedule II controlled substance, as evidenced by an Opioid Risk Tool (ORT)² score ≥ 8 and review of the California Prescription Control Monitoring Program (PDMP) Controlled Substance Utilization Review and Evaluation System (CURES) report demonstrates multiple prescribing providers and/or multiple pharmacies in the last 30 days.

Study Product(s), Dose, Route, Regimen
	
Lazanda (fentanyl) nasal spray is supplied as a 5-mL bottle containing 8 sprays of 100 mcL of solution containing either 100 mcg or 400 mcg fentanyl base. Lazanda will be self-administered intranasally by subjects participating in this study. Subjects will undergo dose titration with Lazanda to determine the minimum effective and tolerable dose during their radiation simulation visit. This dose will be used as pre-medication prior to any further radiation therapy.

Duration of administration
	
Subjects will receive Lazanda at their radiation simulation visit and again as pre-medication prior to each radiation treatment (fraction), for an estimated treatment period of 10 days based on the patient's radiation treatment plan.

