	Screening (≤21 days from baseline)	Radiation Therapy Simulation ⁷ (≤14 days RT)	Radiation Fraction (Daily, up to 10 fractions)	Post Treatment Follow-Up (Daily, for 2 days)
Informed consent	X			
Medical and surgical history	X			
Demographics	X			
Eligibility criteria	X			
ECOG Performance status	X	X	X	
Document location of bone lesion	X			
Pregnancy test (if applicable) ¹	X			
Physical exam	X	Per routine care frequency		
Vital signs	X	Per routine care frequency	Per routine care frequency	
Weight	X	X	X	
Concomitant medications		X	X	X
Adverse events		X	X	X ⁴
Comprehensive metabolic panel	X ⁵	Per routine care frequency		
Record baseline 24-hour opioid dose	X			
Record total time in radiation therapy unit		X	X	
Record recumbent time		X	X	
Lazanda dispensing & administration		X ⁶	X ⁶	
Radiation Therapy (hypofractionation)			X	
Study drug diary		X	X	
Brief Pain Inventory Short Form	X	X	X	X
Numerical Rating System Pain Score ²		X	X	X
Patient medication use diary ³	X	X	X	X
Patient nausea/vomiting diary		X	X	X
Patient laxation diary		X	X	X

- 1) Females of childbearing potential only; must be performed within 72 hours of baseline.
- 2) NRS Pain Score will be collected at a total 2 events: (1) radiation therapy simulation, and (2) at each radiation fraction (up to 10 fractions total). At each event, NRS pain scores will be recorded at T-15 (15 minutes prior to laying down on treatment surface), T0 minutes (laying down on treatment surface), and T+15 after laying down on the treatment surface. (Appendix I- NRS Scale log)
- 3) To include a record of any anticancer therapy, vitamins, homeopathic/herbal remedies, nutritional supplements, opioid medication use, over-the-counter analgesics, and all other over-the-counter and PO medication use.
- 4) Patients will be monitored for adverse events until 30 days following the last study drug administration.
- 5) Serum chemistries performed within six weeks of baseline may be used to fulfill screening requirements.
- 6) Lazanda will be self-administered by the subject 15 minutes (± 5 minutes) prior to laying on the hard surface.
- 7) If the 100-mcg dose does not achieve adequate pain control at the first assessment of the simulation visit, the subject will receive a second dose 2 hours later as per label until the optimal dose is obtained. If not practical the subject will delay or reschedule the next assessment of the simulation (within a 14 days period) or XRT delivery.

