In comparison to morphine sulfate IR, higher PID scores and a greater proportion of patients achieving >33% or >2 point pain intensity score reduction have been reported with Lazanda[®].^{14,15} In one study, pain intensity difference at 15 minutes (mean \pm SD) was 3.0 ± 0.2 and 2.7 ± 0.2 (p<0.05) for Lazanda and morphine sulfate IR, respectively.¹⁵ Decreases in pain intensity by 2 or more was seen in 52.4% and 45.4% of patients (p<0.05) 10 minutes after Lazanda and morphine sulfate IR administration.¹⁴ In another study, PI scores after 5 minutes

(5.6 vs. 5.8) and after 20 minutes (3 vs 3.4) were significantly lower for Lazanda versus intranasal fentanyl. Five minutes after administration, more patients experienced a >33% pain intensity reduction (~13% vs. <5%; $p < 0.05$), while at 20 minutes after administration, more patients experiences a >50% pain intensity reduction (~71% vs. ~55%; $p < 0.05$) with Lazanda.¹⁶

Common adverse events are drowsiness, nausea, vomiting, and constipation, with most these symptoms mild to moderate in severity. Nasal symptoms, including obstruction, discomfort, itching, sneezing, dryness, and crusting have also been mostly reported as mild and moderate in severity.¹²⁻¹⁷ Ninety-nine serious adverse events have been reported in 3 studies, with 25 of these deemed related to fentanyl pectin nasal spray.^{12,15,17} Two deaths possibly related to fentanyl pectin nasal spray have been reported.^{15,17} In one death, the patient developed cyanosis, loss of consciousness, and upper airway obstruction after an apparent unintentional overdose during a breakthrough pain episode.¹⁷

The initial starting dose for this study will be Lazanda 100 mcg prior to radiation therapy simulation. A 100 mcg dose is the initial dose of Lazanda for all patients as detailed in the product package insert. Lazanda dose titration will follow the guidelines as indicated in the product package insert from the baseline visit through the end of radiation therapy. If the subject does not experience relief after 30 minutes, he or she may take another 100 mcg but must wait at least 2 hours from the first spray before administering this second 100 mcg dose.

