4.2.2 Radiation Treatment Visits

Lazanda will be self-administered by the subject while attending their visit to the radiation treatment center, and will be monitored closely by the clinic staff and study coordinator. Therefore, the chance for a missed dose is rare. However, should a subject miss a Lazanda dose prior to treatment fraction, he or she will be instructed to take the dose as soon as it is remembered on the same day prior to radiation.

The dose used as pre-medication prior to any radiation therapy fractions is as described in the titration schema listed above in section 4.2.1 and described in Table 1.

If a patient takes less than the minimal effective dose of Lazanda, they should be monitored closely for evidence of opioid withdrawal symptoms and reversal of central analgesic effects. In cases of known or suspected overdose, symptomatic treatment as well as monitoring of vital functions will be performed. In cases of severe intoxication, intensive care procedures will be completed. Close medical supervision and monitoring will be continued until the patient recovers.

Subjects will be required to record each self-administered dose of Lazanda on a Study Drug Diary (**Appendix H**) from the time of the radiation simulation visit through the end of radiation therapy. Details of Lazanda administration, including date and time of administration as well as number of sprays administered and total daily dose will be recorded by the subject on the Study Drug Diary.

Lazanda will be dispensed to the patient in nasal spray bottle format, within a child-resistant outer container. The child-resistant container should be opened just prior to initial product use. Subjects will be instructed to replace the bottle in the child-resistant container and out of reach of children between doses. Subjects will also be instructed to avoid consumption of grapefruit or grapefruit juice as this is a potent inhibitor of the CYP3A4 enzyme.

There are additional no requirements for monitoring of vital signs or other parameters following Lazanda administration. Treatment with Lazanda does not require that any pre-treatment parameters be met prior to dispensing and/or administration. However, subjects will be advised not to drive during study participation and must be accompanied to all treatments.

Any adverse events or serious adverse events resulting from known or suspected overdose will be reported according to instructions in **Section 7.6** of the protocol.

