4.5 Prohibited concomitant therapy

Unless there is a need for urgent intervention, additional medication for pain control will not be allowed without prior approval from the principal investigator. This includes over-the-counter treatments for pain. Concomitant use of a monoamine oxidase inhibitor is prohibited. Other investigational therapies must not be used while the patient is on the study. If such agents are required for a patient then the patient must be discontinued from the treatment portion of the study.

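### Section 4.2.1 tells subjects to treat later pain episodes with Lazanda, although the plan is visit-only and nothing bars use between visits; its titration-day limit also has two readings

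*Combined protocol and SAP*

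**What the plan says.** **Where Lazanda is used.** The Study Summary (duration of administration), note 6 of the Schedule of Events and section 4.2.1 place Lazanda at simulation and then before each fraction, about 15 minutes before the subject lies down. Section 4.2.2 gives the setting: "Lazanda will be self-administered by the subject while attending their visit to the radiation treatment center", with clinic staff and the study coordinator monitoring closely.

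**The sentence that does not fit.** In the titration bullets of section 4.2.1, if 100 mcg gives adequate analgesia within 30 minutes, "subsequent pain episodes will be treated with this dose".

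**Where the bottle is kept.** Section 4.2.2 dispenses the bottle to the subject, and section 8.1 has it stored securely at home after each use.

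**Titration and its limit.** The dose titration table in section 4.2.1 has steps of 100, 200 and 400 mcg, with at least 2 hours between escalations. Section 1.2 also lets a subject without relief repeat the first step: "he or she may take another 100 mcg but must wait at least 2 hours from the first spray". The limit is "A maximum of 4 doses or 400 mcg allowed per day". A step that does not fit can be moved: "The subject may delay or reschedule the simulation (within a 14 days period) or radiation delivery to achieve the adequate pain control dose". Note 7 of the Schedule of Events says much the same: "the subject will delay or reschedule the next assessment of the simulation (within a 14 days period) or XRT delivery".

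**The concern.** The protocol uses the word episodes for breakthrough pain: section 4.4 counts breakthrough episodes per day, and section 1.2 gives breakthrough cancer pain as the product's indication. A subject or coordinator who follows the section 4.2.1 sentence literally could treat a breakthrough episode at home with the study bottle. The plan contains no such dose.

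The drug is a Schedule II opioid. Section 1.2 reports a death after an apparent unintentional overdose during a breakthrough pain episode, and Appendix B allows strong CYP3A4 inhibitors, which raise fentanyl levels. In that setting the instruction to the subject should be explicit.

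The daily limit is a second, separate wording problem in the same bullets. If a subject has had 100 and then 200 mcg without relief, one coordinator could give 400 mcg that day and another could send the subject to a second day. Both could say they had followed section 4.2.1.

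**Working it through.** **Part 1: use between visits.** No arithmetic applies, so I set the texts side by side.

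| Place | What it settles | What it leaves open |
|---|---|---|
| Study Summary; Schedule of Events note 6; 4.2.1 after the titration table | The titrated dose is pre-medication before fractions | Does not exclude other use |
| 4.2.2 | Doses are taken at the centre, under staff monitoring | Describes the setting; no prohibition |
| 4.4 | Many participants have an as-needed immediate-release opioid for breakthrough pain; above 4 episodes a day, short- and long-acting opioids are re-titrated | Does not mention Lazanda for this purpose, for or against |
| 4.5 | "additional medication for pain control will not be allowed without prior approval from the principal investigator" | Does not name Lazanda |
| Appendix H | A forgotten dose is skipped until the next radiation visit | Covers only forgotten doses |
| 4.2.1, relief at 100 mcg | Later pain episodes are treated with this dose | Conflicts with the rows above |
| 8.1 | The bottle is kept at home | Gives the means for use between visits |

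Every row but the last two points to visit-only use, and none states it as an instruction to the subject.

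**Part 2: the daily limit.** Inputs, all from section 4.2.1: steps of 100, 200 and 400 mcg; at least 2 hours between doses; a limit of 4 doses or 400 mcg per day.

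*The plan's own figure.* At the starting dose, 4 × 100 = 400 mcg, so the two halves of the limit agree. Above 100 mcg they no longer do.

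*One-day titration.* Total = sum of the doses; minimum time from first to last dose = (number of doses − 1) × 2 hours.

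| Path | Doses | Total (mcg) | Minimum time | Limit read as up to 4 doses | Limit read as 400 mcg |
|---|---|---|---|---|---|
| Titration table only | 3 | 100 + 200 + 400 = 700 | 2 × 2 = 4 h | allowed | not allowed |
| With the second 100-mcg dose | 4 | 100 + 100 + 200 + 400 = 800 | 3 × 2 = 6 h | allowed | not allowed |

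*What the 400-mcg reading permits on the first day.* Table path: 100 + 200 = 300; adding 400 would make 700, so the last step moves to another day. With the second 100-mcg dose: 100 + 100 + 200 = 400; adding 400 would make 800, so again it moves.

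*Difference between readings on the first day.* 700/300 = 2.3 and 800/400 = 2.0.

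*Fraction visits.* One dose of at most 400 mcg satisfies both readings, so the ambiguity affects titration days only.

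*Redundancy.* If neither half may be exceeded, the four-dose half never binds on its own, because the smallest dose is 100 mcg and 4 × 100 already reaches 400.

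**The case against.** The case for leaving the text alone is reasonable. The pain-episode sentence sits under a heading about simulation visits, and sections 1.1.3 and 1.3 describe pain on the treatment table as the acute, episodic pain to be treated. Section 4.2.1 itself later says the titrated dose is pre-medication. Pain between visits already has other drugs assigned to it in section 4.4. Controls are substantial: REMS enrolment, opioid-risk and prescription-database screening, no surplus bottles, every dose recorded in the diary, unused drug brought to each clinic visit (section 8.1.2), and return and destruction at the end. All of this stands, and it limits the risk. Diary checks and reconciliation, however, detect extra use afterwards; they do not tell the subject to avoid it.

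On the limit, the natural reading is that neither half may be exceeded. That reading works, because deferral is already allowed. Sections 1.2 and 4.1 and note 7 of the Schedule of Events also defer to the package insert or label, which is not in the documents and may settle the matter. This stands too, and it is why the point is ambiguity and not error.

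Four stronger inferences are tempting, and the documents do not support them:

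- *That the protocol intends home use of Lazanda.* One sentence points that way; the rest of the dosing text points to visits.
- *That the daily limit also conflicts with visit-only use.* It belongs to the titration bullets, where several doses in a day are planned.
- *That four doses at the higher steps, or the quantity left in the bottle, measure the exposure.* Neither one pass of titration nor a single pre-fraction dose repeats a higher step four times, and the supply at home depends on dispensing decisions the text leaves to the investigator.
- *That the trial's results are compromised.* Nothing in the documents shows that use between visits is expected.

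**Conclusion.** The concern holds as a conflict of wording with a safety consequence. The sentence on later pain episodes contradicts a plan that is otherwise visit-only, and the explicit instruction that would neutralise it is absent from the available text. Consent pages are not part of that text, so an instruction there cannot be ruled out; the protocol and the diary should carry it in any case.

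The limit on titration days is ambiguous above 100 mcg: a one-day total of 700 or 800 mcg is allowed under one reading and forbidden under the other. This part is less certain, because the package insert could resolve it. The figures assume that titration goes as far as the 400-mcg step; how many subjects will need that is not stated.

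Both parts should be corrected. The endpoint, sample size and analysis model are unaffected.

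**What to change.** 1. In section 4.2.1, replace the pain-episode wording with: *subsequent simulation and pre-fraction doses will be this dose*.
2. Add to section 4.2.2 and to the Appendix H instructions: *Lazanda must not be used outside the simulation visit(s) and the radiation treatment visits*.
3. After checking the package insert, state the limit as *4 doses or 400 mcg per day, whichever is reached first*, and add that a step which would exceed it is given on another day, by rescheduling the simulation or delaying radiation delivery as section 4.2.1 already allows. Do not tie the deferred step to the 14-day simulation window alone, because radiation delivery may also be delayed, and sections 4.1 and 4.2.1 allow titration or dose adjustment later. Keep the second 100-mcg dose as it is.

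The cost is three wording edits, approved as an amendment under section 10.10. Edit 3 means a second titration day for any subject who needs 400 mcg: anywhere from 0 to 6 of the 6 subjects in the Study Summary, since the documents give no expected share.
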